#### **11.4. Guidelines for Recording Adverse Events**

Each reportable AE should be documented as a single medical diagnosis. If this is not possible, the signs or symptoms should be documented until a medical diagnosis is identified. If an AE resolves and reoccurs at a later date, a new AE must be documented and reported as appropriate. The following guidelines should be followed to improve the quality and precision of AE data:

- Recognized medical terms (not colloquialisms, abbreviations, or jargon) should be used when recording AEs
- The diagnosis (i.e., disease or syndrome) should be recorded instead of signs and symptoms (e.g., pneumonia instead of shortness of breath, coughing, and fever)
- Any sign or symptom considered as unrelated to an encountered disease or syndrome should be recorded as an individual AE (e.g., if nausea and severe headache are observed at the same time, each event should be recorded as a separate AE)
- Adverse events occurring within 30 days after EOT should be reported.

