### 5.2.3 Consolidation

Consolidation therapy is not defined by the protocol. Patients achieving CR/CRi will proceed with consolidation therapy and/or hematopoietic stem cell transplantation at the discretion of the treating physician in accordance with institutional practice.

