### 5.3. End of Treatment

End of treatment procedures will be performed for all patients when study treatment is discontinued for any reason or another AML therapy is started, including conditioning regimens for transplantation. Every reasonable effort will be made to complete the procedures to prevent loss to follow up. A separate visit may not be required, and the procedures performed at the last visit may satisfy the required end of treatment procedures. Ongoing serious adverse events (SAEs) assessed by investigators as related to study treatment will be followed with reasonable effort until the event resolves, stabilizes, is considered irreversible, or the patient receives a new AML therapy or dies.

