### 11.3. Assessment and Recording of Adverse Events

All AEs grade 3 or higher occurring during the reporting period must be assessed and recorded as follows:

- Name of the event (diagnosis preferred, otherwise state signs and symptoms)
- Date of onset and stop date (if available)
- Course (i.e., intermittent, ongoing)
- Maximum intensity or severity (grade) based on the NCI CTCAE version 4.03
- Relationship to study treatment
- Seriousness
- Outcome
- Use of concomitant medication to treat a patient for an AE

**Adverse events of special interest that occur at grade 1 or higher will be recorded. Adverse events of special interest are: mucositis, infection, neutropenia, diarrhea, and thrombocytopenia.**

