### 12.6. Safety Analysis

Adverse events and laboratory data will be graded according to the NCI CTCAE version 4.03. As described above frequency and percentage of patients will be summarized for any adverse event by grade, attribution, organ class, and preferred term overall and by patient. Change in continuous laboratory data from just prior to therapy and by visit will be summarized by frequency of abnormal values. Linear and non-linear regression will be used to model changes over time, accounting for intra-patient correlation using mixed models or GEE, as appropriate.

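### No rule separates adverse events that begin after non-protocol AML therapy starts, so the any-AE summaries can mix its toxicity with that of 7+V

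*Combined protocol and SAP*

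**What the plan says.** On the reporting window, section 11.4 says: "Adverse events occurring within 30 days after EOT should be reported". Section 5.3 calls for EOT procedures when "study treatment is discontinued for any reason or another AML therapy is started, including conditioning regimens for transplantation". Section 8.1.3 lists both completion of the maximum allowed treatment and the start of other systemic AML therapy as reasons for discontinuing study treatment.

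On what follows induction, section 5.2.3 says "Consolidation therapy is not defined by the protocol" and continues: "Patients achieving CR/CRi will proceed with consolidation therapy and/or hematopoietic stem cell transplantation at the discretion of the treating physician".

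On recording, section 11.3 requires AEs of grade 3 or higher to be recorded, with "Relationship to study treatment" and an onset date among the fields. A further group is recorded from grade 1: "Adverse events of special interest are: mucositis, infection, neutropenia, diarrhea, and thrombocytopenia". Section 11.6 has the investigator attribute toxicity to vosaroxin, cytarabine, other concomitant medication or other medical causes. Table 5 gives a five-level scale from unrelated to definite.

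On analysis, section 12.6 says "frequency and percentage of patients will be summarized for any adverse event by grade, attribution, organ class, and preferred term".

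The one place where new AML therapy acts as a boundary is section 5.3, which ends follow-up of ongoing treatment-related SAEs at that point.

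**The concern.** Safety and tolerability of 7+V is the first secondary objective (section 2.2). The trial has one arm, so no control group would show that an AE percentage contains toxicity from another regimen. The reporting window can extend into consolidation or conditioning, yet the plan has no treatment-emergent definition and no cut-off at new therapy for AEs that begin later. The events captured most widely, from grade 1, could plausibly also be caused by further intensive chemotherapy, so causality is hardest to judge where capture is broadest. An any-cause table for such events would then describe 7+V plus whatever followed it, to an extent that varies with local practice.

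**Working it through.** The documents give no safety threshold, expected AE rate or safety sample size for this point, so there is no planned figure to reproduce. The check is a reading of the sections together, followed by sizing under stated assumptions.

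**1. Does any rule cut or split new AEs at new therapy?** Sections 5.3, 11.3, 11.4, 11.6, 12.6 and the Table 1 footnotes were compared. The only stop at new AML therapy is the section 5.3 rule on ongoing related SAEs. It does not apply to events that start afterwards.

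**2. How far can the window overlap new therapy?** Let g be the days from EOT to the start of new therapy. Overlap = max(0, 30 − g).
- If the start of new therapy sets EOT, g = 0 and the overlap is 30 days.
- If EOT is dated earlier, the overlap shrinks: g = 10 gives 20 days, and g ≥ 30 gives none.

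The documents do not say which trigger dates EOT. Counting from day 1 of a single induction:

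| EOT dated at | Source | Window ends about day |
|---|---|---|
| Last cytarabine dose, day 7 | section 3.1 | 7 + 30 = 37 |
| Count recovery, 5-6 weeks (days 35-42) | section 5.2 | 65-72 |
| Latest EoT, day 57 | Table 1, footnote j | 87 |

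These readings differ by up to 87 − 37 = 50 days. Under the later two, the tail falls when assessed responders can move to consolidation. Footnote p adds to the uncertainty by waiving EoT activities when disease assessment was already done at count recovery.

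**3. How many patients?** N = 41 and CR rates of 40% and 60% come from section 3.1.
- Complete responders: 41 × 0.40 = 16.4 and 41 × 0.60 = 24.6, so about 16-25. CRi patients would add to this.
- The share s starting non-protocol therapy within the window is not given. Assumed values:

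| s | 40% CR | 60% CR |
|---|---|---|
| 25% | 4.1 | 6.15 |
| 50% | 8.2 | 12.3 |
| 100% | 16.4 | 24.6 |

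**4. What could it do to an any-cause percentage?** Let q be the true event rate under 7+V, c the CR rate, and e the chance that new therapy causes the event independently within the window. Any-cause rate = q + (1 − q) × c × s × e. Take q = 30% and e = 10-20%, both assumed.
- s = 100%: 0.30 + 0.70 × 0.40 × 0.10 = 0.328, to 0.30 + 0.70 × 0.60 × 0.20 = 0.384.
- s = 50%: 0.30 + 0.014 = 0.314, to 0.30 + 0.042 = 0.342.

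For comparison, the approximate 95% half-width for 30% at n = 41 is 1.96 × √(0.30 × 0.70 / 41) = 0.14.

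**5. Does attribution separate the sources?** In part. Tables restricted to related events exclude post-therapy events unless they are misattributed. Section 11.6 does not name subsequent AML therapy, so it must fall under one of the two residual categories. If consolidation contains cytarabine (assumption), the cytarabine category does not say which course is meant. Counts made regardless of attribution include these events in every case.

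**6. Is the window consistent with the calendar?** Footnote c of Table 1 ties AE reporting to calendar days and captures events between visits under the criteria of section 10. The AE row, as the table can be read, has no entry under EoT. This needs reconciling with the 30-day window in section 11.4.

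**The case against.** A reader might infer that toxicity of consolidation or conditioning is simply counted as 7+V toxicity. The documents do not support that. Relationship to study treatment is recorded for each reportable AE, section 11.6 includes the open category of other medical causes, and section 12.6 tabulates by attribution. Study treatment is limited to at most two inductions (section 5.2), so investigators have no instruction to charge consolidation to it. This part of the defence stands.

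A reader might also infer that the whole 30-day tail always lies on non-protocol therapy. That holds only if the start of that therapy sets the EOT date.

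Nor do the documents show that AE rates must rise with efficacy. The new-therapy trigger in section 5.3 applies to everyone, and non-responders who start other AML treatment have the same mixed window. Section 5.2.3 makes further therapy the expected course for responders, so a tendency is plausible, but no more than that.

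The effect may also be small. The assumed rise is well inside the sampling uncertainty. A patient who already had the event at that grade adds nothing to a percentage of patients, and section 7 expects most patients to have neutropenia, thrombocytopenia or both at entry. AE onset dates and transplant status are already collected, and wide collection is the cautious direction for safety.

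What remains is that the any-cause summaries have no rule for events after new therapy, the EOT date is undefined, and no start date for consolidation is specified for recording.

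**Conclusion.** The gap is real but minor. As written, the section 12.6 any-AE summaries can mix toxicity of 7+V with that of later non-protocol therapy; attribution reduces this without removing it. Up to about 16-25 of 41 patients could have a mixed window at 40-60% CR if every complete responder starts new therapy within it, and about 4-12 if 25-50% do. Those shares are assumptions. The movement of a 30% rate to 33-38% is an illustration at the upper range, since it takes every complete responder as starting within the window and uses assumed event rates; it is not an estimate for this trial. The CR endpoint, type I error, power and sample size do not depend on this point.

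**What to change.** Leave AE collection and SAE reporting as they are, through 30 days after EOT. Then:

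- In sections 5.3 and 11.4, state which event sets the EOT date.
- Record on the CRF the start date of the first non-protocol AML therapy, conditioning included.
- In section 12.6, base the main 7+V AE summary on events with onset from first dose to the earlier of two dates: 30 days after EOT, or the day before that therapy starts. Tabulate later-onset AEs separately as occurring after subsequent AML therapy. Keep attribution in both tables.
- Reconcile section 11.4 with the calendar-day rule in Table 1 and its footnote c.

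The analysis window should not be closed at 30 days after the last dose. For a single induction that is about day 37, before the end of the 5-6 week recovery period expected in section 5.2 and before the day-57 and 8-week toxicity limits in section 8.1.3, so genuine late 7+V toxicity could be lost even in patients with no further therapy.

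The cost is a few sentences and one CRF date. The downside is that late 7+V events starting after new therapy appear in the second table, where they remain visible with their attribution.

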#### **11.5. Intensity of the Adverse Event**

The investigator will grade each reportable AE based on its maximum intensity (or severity) using the NCI CTCAE V4.03 (available at: <http://evs.nci.nih.gov/ftp1/CTCAE/About.html>). If no grading criteria are provided for the AE, it should be graded using the scale presented in Table 5, noting that not all grades are appropriate for all AEs.

#### **11.6. Adverse Event Attribution**

The investigator will determine the attribution of toxicity relative to the vosaroxin, cytarabine, other concomitant medication, or other medical causes in accordance with the ICH E2A guidelines.

**Table 5. Definition of Adverse Event Attribution**

Attribution	Description
Unrelated	The AE is clearly NOT related to the intervention.
Unlikely:	The AE is doubtfully related to the intervention.
Possible:	The AE may be related to the intervention.
Probable:	The AE is likely related to the intervention.
Definite:	The AE is clearly related to the intervention.

### 11.7. Serious Adverse Event Reporting Requirements

Study site personnel must report all SAEs by fax as soon as possible to the Coordinating Center, but within 1 business day of first becoming aware of the SAE. The following minimum information is required by the sponsor:

- Patient identification (i.e., study number, sex, age)
- Description of the SAE (diagnosis preferred, symptoms, etc.)
- Investigator name
- Study drug and causal relationship of the SAE to the study drug(s)

The SAE report should be submitted via secure email transfer or via fax using the contact information listed below:

Attn: VICC Multi-Institutional Coordinating Center

[contact]

or

[contact]

Transmission of the SAE report should be confirmed by the site personnel submitting the report.

Follow-up information for SAEs and information on non-serious AEs that become serious should also be reported to the Coordinating Center as soon as it is available; these reports should be submitted using the SAE Report Form.

Investigators must submit written safety reports as required by their Institutional Review Board (IRB) or Institutional Ethics Committee (IEC) within timelines set by regional regulations (European Union common technical document or US FDA). The study site should retain documentation of the submission of expedited safety reports to the IRB/IEC, and their receipt.

Persistent or recurrent AML (or “disease progression”), including AML leading to death, should not be recorded as an SAE. Persistent or recurrent AML is an outcome of treatment and will be documented as treatment failure. Associated events resulting from persistent or recurrent AML (or “disease progression”) should be recorded as AE or SAEs, and SAEs resulting in death should be documented.

## 11.8. General Instructions for Reporting Serious Adverse Events to the FDA and Sunesis Pharmaceuticals

### Food and Drug Administration (FDA)

FDA regulations and statutory provisions establish adverse event reporting requirements for human drugs. These requirements apply to the manufacturer of the product in question. In general, manufacturers of prescription drugs marketed for human use are required to submit postmarketing safety reports of adverse drug experiences to FDA.a A report of each adverse drug experience that is both serious and unexpected must be made to FDA as soon as possible, but no later than 7 days for a life-threatening or fatal event, and 15 days for all others after receiving information about the event.b Persons required to file such 15-day Alert reports are also required to investigate and submit any new information to FDA.c The Sponsor is responsible for reporting SAEs to the FDA.

SAE supporting documents, such as a discharge summary or pertinent laboratory data may be provided; however, the study personnel should not wait to receive complete information before notifying the Coordinating Center of an SAE. The study site is responsible for requesting pertinent follow-up information missing from initial reports and forwarding the information within 24 hours of receipt. The Coordinating Center may request additional information if necessary.

a 21 C.F.R. §§ 310.305(c); 314.80(c); 314.98 (human drugs), 600.80(c) (biologics). To avoid duplication of reports, non-applicant manufacturers, packers, and distributors of drug and biological products having an approved application may submit all reports of serious adverse drug experiences to the applicant within 5 calendar days of receipt of information about the event, rather than submitting reports to FDA. See 21 C.F.R.

§§ 314.80(c)(1)(iii), 600.80(c)(1)(iii). Similarly, packers and distributors of prescription drug products marketed for human use without an approved application may meet their post-marketing 15-day safety reporting obligations under 21 C.F.R. § 310.305 by submitting all reports of serious adverse drug experiences to the manufacturer within 5 calendar days of the receipt of information instead of reporting to FDA. Applicants/manufacturers receiving such data must then, in turn, submit a 15-day Alert report to FDA.

b 21 C.F.R. §§ 310.305(c)(1); 314.80(c)(1)(i); 314.98(a) (human drugs), 600.80(c)(1)(i) (biologics). There are also certain specific reporting requirements concerning fatalities related to blood and blood products. 21 CFR §§ 606.170(b), 640.73.

c 21 C.F.R. §§ 310.305(c)(2), 314.80(c)(1)(ii), 314.98(a) (human drugs), 600.80(c)(1)(ii) (biologics).

### Sunesis Pharmaceuticals

The Sponsor will report all SAEs regardless of causal relationship to study treatment to Sunesis.

## 12. STATISTICAL METHODS AND DETERMINATION OF SAMPLE SIZE

### 12.1. Statistical Considerations

The primary objective of this single-arm, phase II clinical trial is to determine if Vosaroxin, in combination with standard dose cytarabine as induction chemotherapy, can significantly improve the rate of complete remission (CR) in patients with untreated acute myelocytic leukemia. Forty-one (41) patients will be enrolled in a two-stage design that permits one interim look to examine evidence of futility. As per convention, the study will not be stopped early on the basis of preliminary evidence of efficacy observed at the end of the first stage (i.e., at the interim look).

### 12.2. Sample Size Considerations

In accordance with our desire to maintain a uniform study design, we set a total sample size of 41 participants. An interim futility analysis will be conducted following enrollment of 17 evaluable patients. If  $\leq 7$  patients achieve CR then the likelihood ratio in support of reaching the goal endpoint of  $\geq 60\%$  remission would be diminished and the data would then be reviewed by a DSMB to determine if further enrollment is warranted. If  $> 7$  CRs are experienced by the first 17 evaluable patients, enrollment will automatically proceed to enroll a total of 41 patients. Under this two-stage design, a 60% complete remission rate by the “7+V” combination is at least 3.375 times more likely than a 40% CR rate if 22 or more patients experience CR.

In the context of the planned likelihood assessment the option will be provided to add an extension cohort of up to 20 participants if the initial trial results are inconclusive. The use of a likelihood based extension cohort results in false positive and false discovery rates of 3.7% and 3.9%, respectively.

### 12.3. Study Design

*Overview:* Two-stage single-arm phase II designs with a single interim look for futility are common in this setting. Simon’s optimal two-stage design is a classic design and remains a popular choice. Herein we propose, in the context of a standard two-stage design, that a likelihood-based assessment of the statistical evidence be used. The unique and informative assessment of the observed evidence provided by likelihood ratios is reason enough to employ the approach.

We will employ the likelihood ratio (LR), not a tail area probability (p-value), to represent the strength of statistical evidence with respect to either a 40% or 60% true CR rate. Likelihood ratios are positive and a LR of 1 indicates completely neutral evidence. Small likelihood ratios ( $LR \ll 1$ ) indicate evidence for the null hypothesis and large likelihood ratios ( $LR \gg 1$ ) indicate evidence for the alternative. The scale of evidence is truly continuous, mapping a gradual shift from weak to moderate to strong evidence.

An important advantage is that, unlike p-values, likelihood ratios have three evidential zones: evidence favoring the null hypothesis, evidence favoring the alternative hypothesis, and weak or inconclusive evidence (i.e., favoring neither hypothesis). Of course, p-values have only two zones: evidence against the null hypothesis ( $p < 0.05$ ) and inconclusive evidence ( $p > 0.05$ ; large p-values do not constitute stronger evidence in favor of the null hypothesis). Moreover, the likelihood false discovery rate is easily quantifiable as  $1/(LR+1)$ . Thus, an observed likelihood ratio of 4 (supporting the alternative) has a false discovery rate of 20%. Lastly, likelihood designs have excellent operating characteristics.

*Parameters and assumptions:* For planning purposes, we assume the complete remission rate of standard induction chemotherapy is 40% in the targeted population of this trial and that the use of Vosaroxin in combination with cytarabine may increase this rate to 60%. We plan to enroll a total of 41 patients, but provide the option of adding an extension cohort of 10 to 20 participants if the initial trial results are inconclusive.

*Two-stage single-arm phase II designs:* There are many two-stage designs that meet nominal Type I and II Error criteria. We choose a two-stage design with a slightly increased expected sample size (EN) of 25.6 but keeps the two-stage sample size below that of a single-stage study ( $n=42$ ) as follows: In stage I, 17 patients are accrued and the study is stopped only if 7 or fewer patients experience a complete remission (CR). Stopping in this fashion is interpreted as evidence of futility. If 8 or more patients experience a CR, the study continues to accrue an additional 24 participants (for a total of 41). At the end, the study is said to generate evidence in support of the hypothesis that incorporating Vosaroxin into frontline AML induction chemotherapy is worthy of future study if 22 or more patients experience CR (i.e. if the observed response rate is greater than 53%). If frontline induction therapy with Vosaroxin plus standard dose continuous infusion cytarabine fails to improve upon the historical CR rate of 40% with conventional 7+3 induction therapy, the study has a 64% probability of early termination (PET).

A standard (frequentist) two-stage design is unable to handle deviations from its planned design (i.e., when the sample size is anything other than 17 or 41). This occasionally happens in multi-center clinical trials for practical reasons relating to the speed of communication and clinical expediency. Green and Dahlberg introduced flexible designs to that are able to accommodate such deviations from planned designs with minimal impact to their nominal operating characteristics. However, in this case, the Green and Dahlberg criteria result in a 25% PET, which poorly protects patients from ineffective therapy. This is one motivating factor in our choice of employing a likelihood-based assessment of the evidence. The likelihood ratio reveals alternative interim stopping criteria that maintain nominal Type I and Type II Error rates, adding significant logistic flexibility (Table 6). Within the context of standard two-stage design, we believe our proposed design best balances the probability of early termination and expected sample size under the stated constraints.

**Table 6.** Interim stopping rules that are constrained to lie between 30% and 60% of total accrual and have a probability of early termination that exceeds 50%. Type I & II Error rates are below designed nominal levels (5% & 20%).

Observed CRs in stage I	Stage I sample size	Probability of early termination	Expected sample size	Likelihood ratio favoring null that corresponds to Simon's futility stopping rule
7	17	64%	25.6	1/3.375
8	19	67%	26.3	1/3.375
9	21	69%	27.2	1/3.375
10	23	71%	28.2	1/3.375
6	16	53%	27.8	1/5.062
7	18	56%	28.2	1/5.062
8	20	60%	28.5	1/5.062

*Likelihood assessment of evidence:* In accordance with our desire to maintain a uniform study design, we set a total sample size of 41 participants, a 17 patient first stage, and an interim futility criterion of 7 or fewer CRs with the added flexibility at the interim analysis indicated in table 1. The interim futility criterion translates to stopping the study at the end of the first stage if the observed likelihood ratio is less than 1/3.375 (i.e., if the evidence better supports the null hypothesis by a factor of at least 3.375). The likelihood ratio is defined as  $LR = \theta_1^r (1 - \theta_1)^{n-r} / \theta_0^r (1 - \theta_0)^{n-r}$  where  $r$  is the number of CR's among  $n$  patients treated and  $H_0: \theta = \theta_0 = 0.4$ ,  $H_1: \theta = \theta_1 = 0.6$ . The translated stopping LR's for the competing designs are listed in the last column of table 1.

An important aspect of the likelihood assessment is that it can quantify the reliability of an observed outcome. For example, while the study would stop early with either an observed LR of 1/3.375 or 1/15 (evidence favoring the null hypothesis), the associated false discovery rates of 0.23 (=1/4.375) and 0.063 (=1/16), respectively, distinguish between those results and provide critical information for investigators when interpreting this evidence at the end of the study.

With a likelihood design, it can happen that the trial yields weak or inconclusive evidence. Technically this can happen in all standard (i.e., frequentist) two-stage designs as well, but when it does the standard design forces a ‘call’ of either ‘Reject the null’ or ‘Fail to reject the null’ (the assignment depends on how the Type I Error is spent throughout the study and can lead to some uncomfortable circumstances, such as calling evidence supporting the alternative as ‘Fail to reject’ and vice versa). Hence, in likelihood designs, it is desirable to minimize the chance of observing weak evidence. Our proposed two-stage design accomplished this sufficiently, as we next describe, but the important thing to remember is that if the trial does result in weak evidence there is no penalty for accruing additional subjects and reporting the combined evidence (assuming that resources will allow such action). In a likelihood design, the probability of weak evidence is driven to zero by the sample size, so it is always possible to refine inconclusive results, often within limited resource constraints.

Table 7 displays a simulation of the proposed trial, potential outcomes, and their probability of occurrence. Analytic expressions for these probabilities exist, but simulating is simpler and essentially as accurate. Table 2 shows what we expect to happen, on average, for our proposed design and what happens if the sponsor chooses to add patients at the end of the trial to refine weak evidence (if observed). In particular, it shows that the chance of observing weak evidence at the end of the study is ~8%, which can be reduced to ~3% (or ~1%) by adding 10 (or 20) more participants. Importantly, only an additional 54 false positives were observed, which represents a very modest inflation in the Type I Error rate from 4.9% (=247/5000) to 6%, and 286 trials under the alternative achieved sufficient evidence to declare efficacy for an increase in power from 80% (=4026/5000) to 86%. At the end of stage II, the false discovery rate for any type of rejection (i.e., any likelihood ratio greater than or equal to 3.375) is 5.8% (=247/(247+4026)). Clearly, cohort expansion can proceed with minimal rates of unwanted consequences.

**Table 7.** Simulation results for extending the likelihood two stage trial for the purpose of refining weak evidence. Cells contain the number (proportion of 5000) trials in each evidentiary class.

Results Under True Ho:						
LR Class	Trials at end of two-stage design	Weak evidence	Add 10 patients	Weak evidence	Add 10 patients	Weak evidence
$LR \leq 1/3.375$	1145		207		105	
$1/3.375 < LR < 1$	260	424 (8.5%)	113	179 (3.6%)	35	58 (1.2%)
$1 < LR < 3.375$	164		66		23	
$LR \geq 3.375$	247		38		16	
Results under true Ha:						
$LR \leq 1/3.375$	143		39		16	
$1/3.375 < LR < 1$	148	397 (7.9%)	48	135 (2.7%)	30	134 (1.1%)
$1 < LR < 3.375$	249		87		26	
$LR \geq 3.375$	4026		223		63	

a 64% (3184) and 8.7% (434) trials stopped early for futility under the true null and true alternative hypotheses, respectively.

Under the likelihood evidentiary paradigm observed results are reported as follows (let  $K > 1$  be the pre-specified LR that maintains a certain false discovery rate): 1) sufficiently strong evidence for the null ( $LR \leq 1/K$ ); 2) actionable weak evidence for the null ( $1/K < LR < 1$ ); 3) actionable weak evidence for the alternative ( $1 < LR < K$ ); 4) sufficiently strong evidence for the alternative ( $LR \geq 1/K$ ). We will also report the FDR for the result at hand, i.e.  $1/(LR+1)$ . As detailed below, this trial may recruit additional participants if the observed LR is weak (i.e.,  $1/K < LR < K$ ) with a maximum of 61 participants.

A significant number (~8%) of discoveries under the null and alternate hypotheses for our two-stage design had LR of exactly 3.375. Though such results would allow the conclusion of sufficient activity to warrant further investigation in more definitive trials because it passes nominal Type I and II Error rate criteria, we propose to further evaluate these results in the extension cohorts by setting  $K=4$ , treating those trials with LR's of 3.375 as weak evidence. The PET remains unaffected by this slight change. However, the design that uses  $K=4$  and a total sample size of 61 patients has a false positive rate that decreases to 3.7% and power that increases to 83.7%. This strategy also decreases the false discovery rate to 3.9% (table 8). Hence such a design is quite feasible.

**Table 8.** Simulation results for extending the likelihood two stage trial for the purpose of refining weak evidence for K=4. Cells contain the number (proportion of 5000) trials in each evidentiary class.

Results Under True Ho:						
LR Class	Trials at end of two-stage design	Weak evidence	Add 10 patients	Weak evidence	Add 10 patients	Weak evidence
LR $\leq$ 1/4	878		307		186	
1/4 < LR < 1	527	813 (16.3%)	299	474 (9.5%)	175	273 (5.4%)
1 < LR < 4	286		175		98	
LR $\geq$ 4	125		32		15	
Results under true Ha:						
LR $\leq$ 1/4	65		20		21	
1/4 < LR < 1	226	833 (16.7%)	170	471 (9.4%)	85	274 (5.5%)
1 < LR < 4	607		301		189	
LR $\geq$ 4	3668		342		176	

a 64% (3184) and 8.7% (434) trials stopped early for futility under the true null and true alternative hypotheses, respectively.

